4 STUDY DESIGN

4.1 Description

This is an open label, non-randomized phase 2 study of the combination of pembrolizumab and cabozantinib to assess overall response rate (ORR), progression free survival at 6 months (PFS6), and overall survival (OS) in patients with metastatic urothelial carcinoma (UC) ineligible for cisplatin. Cabozantinib is administered at 40 mg oral daily. Pembrolizumab will be administered at a fixed dose of 200mg intravenously every 3 weeks for all patients. A safety analysis will be performed after the first 6 patients enroll and receive treatment.

During this stage, the decision to continue enrollment will be made by the Data Safety and Monitoring Committee (DSMC). When all 6 subjects in the have been followed for at least 21 days following first dose of pembrolizumab and cabozantinib, all available safety data will be considered in a decision to continue enrollment. Therapy continues until progression or intolerable toxicities. Study treatment may continue beyond initial radiographic or clinical disease progression as long as the patient is deriving clinical benefit from the treatment, as assessed by the investigator. Patients removed from therapy without evidence of progression will undergo radiological examination every 12 weeks or earlier if clinically warranted.

4.2 Number of Patients

A total of up to 39 subjects will be enrolled with the objective of having a minimum of 35 evaluable subjects for the primary objective.

4.3 Number of Study Centers

This is a multisite study to be conducted at Huntsman Cancer Institute at the University of Utah, Salt Lake City, Utah. Up to two additional sites may be included.

4.4 Study Duration

We anticipate up to 2 years to complete enrollment followed by 1 year of treatment and 5 months follow up. Total duration of the trial will be 3-to-4 years.

4.5 Conditions for Terminating the Study

At any time, the study may be terminated by the study sponsor or by Exelixis as described in the clinical trial agreement.

5 ELIGIBILITY CRITERIA

5.1 Pre-Screening Eligibility for Patients Scheduled for Urothelial Diagnostic Procedure (biopsy or surgery)

This eligibility checklist is used to determine a subject's eligibility for pre-screening correlative tissue collection. It must be filed in the subject's research chart with the enrolling investigator's signature.

Patient No. _____

Patient's Initials: (L, F, M) _____

5.1.1 Inclusion Criteria

Yes/No (Response of "no" = patient ineligible)

5.1.2 _____ Male or female subject aged \geq 18 years.

5.1.3 _____ Clinically, subject is a candidate for urothelial diagnostic procedure (fresh soft-tissue biopsy or TURBT).

5.1.4 _____ Subject meets general medical criteria for consideration of treatment with immunotherapy using a checkpoint inhibitor.

I certify that this patient meets all inclusion and exclusion criteria for enrollment onto the pre-screening portion of this study.

Investigator Signature

Date

Time

This eligibility checklist is used to determine patient eligibility and filed with enrolling physician's signature in the patient research chart.

Patient No. _____

Patient's Initials: (L, F, M) _____

5.2 Inclusion Criteria

Yes/No (Response of "no" = patient ineligible)

5.2.1 _____ Histologically proven transitional cell or urothelial carcinoma.

5.2.2 _____ Patients with locally advanced or metastatic urothelial carcinoma *must meet one of the following:*

- Patients who are not eligible for cisplatin-containing chemotherapy AND whose tumors express PD-L1 (Combined Positive Score (CPS) ≥ 10 as determined by an FDA-approved test
OR
- Patients who are not eligible for any platinum-containing chemotherapy regardless of PD-L1 status.

5.2.3 _____ Metastatic (any N+ or M1) or locally advanced, unresectable (T4bN0) disease.

5.2.4 _____ Measurable disease is required as determined by RECIST v1.1.

5.2.5 _____ Performance Status ECOG 0-2

5.2.6 _____ Cisplatin-ineligibility based on ≥ 1 of the following:

- Estimated creatinine clearance between ≥ 30 and < 60 ml/min (Cockcroft-Gault formula)
- ECOG PS > 1
- Hearing loss
- Baseline neuropathy > grade 1.
- Patient refusal

5.2.7 _____ Be ≥ 18 years of age on day of signing informed consent.

5.2.8 _____ Serum albumin ≥ 2.8 g/dl

5.2.9 _____ Alkaline phosphatase (ALP) $\leq 3 \times$ upper limit of normal (ULN). ALP $\leq 5 \times$ ULN with documented bone metastases.

5.2.10 _____ Negative serum or urine pregnancy test at screening for women of childbearing potential (see section 7.3).

5.2.11 _____ Highly effective contraception for both male and female subjects throughout the study and for at least 120 days after last pembrolizumab treatment administration if the risk of conception exists (section 7.3).

5.2.12 _____ Must have recovered from adverse effects of any prior surgery, radiotherapy or other antineoplastic therapy to grade ≤ 2 . If not recovered to grade ≤ 2 , these must be deemed to be irreversible adverse events related to prior surgery and /or radiation therapy (such as incontinence or sexual dysfunction) per investigator clinical judgment.

5.2.13 _____ Recovery to baseline or \leq Grade 2 CTCAE v.5.0 from toxicities related to any prior treatments, unless AE(s) are clinically nonsignificant and/or stable on supportive therapy. Alopecia, sensory neuropathy Grade ≤ 2 , or other Grade ≤ 2 not constituting a safety risk based on investigator's judgment are acceptable.

5.2.14 _____ Last dose of any radiation therapy > 2 weeks before first dose of study treatment.

5.2.15 _____ Able to provide informed consent and willing to sign an approved consent form that conforms to federal and institutional guidelines.

5.2.16 _____ Adequate organ function as defined as:

- Hematologic:** Absolute neutrophil count (ANC) $\geq 1.5 \times 10^9/L$ (without granulocyte colony-stimulation factor support within 2 weeks of screening), platelet count $\geq 100 \times 10^9/L$ (without platelet transfusion within 2 weeks of screening), hemoglobin ≥ 9 g/dL (may have been transfused), and white blood cell count (WBC) $\geq 2.5 \times 10^9/L$.
- Hepatic:** Total bilirubin level $\leq 1.5 \times$ the upper limit of normal (ULN) ($\leq 3 \times$ ULN for subjects with Gilbert's disease / or unconjugated hyperbilirubinemia) and AST and ALT levels $\leq 2.5 \times$ ULN or AST and ALT levels $\leq 3 \times$ ULN for subjects with documented metastatic disease. Patient with a history of unconjugated hyperbilirubinemia with otherwise acceptable liver enzyme levels (as per above criteria) may have higher bilirubin levels.
- Renal:** Urine protein/creatinine ratio (UPCR) ≤ 2 mg/mg (≤ 113.2 mg/mmol) and serum creatinine $\leq 2.0 \times$ ULN or calculated creatinine clearance ≥ 30 mL/min (≥ 0.5 mL/sec) using the Cockcroft-Gault

equation:

- Males: $(140 - \text{age}) \times \text{weight [kg]} / (\text{serum creatinine [mg/dL]} \times 72)$
- Females: $[(140 - \text{age}) \times \text{weight (kg)} / (\text{serum creatinine [mg/dL]} \times 72)] \times 0.85$

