Proteinuria: Proteinuria has been reported with cabozantinib. Proteinuria should be monitored by measuring UPCR. Table 7.7 provides treatment guidelines for proteinuria deemed related to cabozantinib.

All study treatment should be permanently discontinued in subjects who develop nephrotic syndrome (proteinuria > 3.5 grams per day in combination with low blood protein levels, high cholesterol levels, high triglyceride levels, and edema).

Table 7.7: Management of Proteinuria Associated with Cabozantinib

Severity of Proteinuria (UPCR)	Management of Proteinuria
≤ 1 mg/mg (≤ 113.1 mg/mmol)	
 • No change in cabozantinib treatment or monitoring

> 1 and < 3.5 mg/mg (> 113.1 and < 395.9 mg/mmol)	
Consider confirming with a 24-h protein assessment within 7 daysNo change in cabozantinib treatment required if UPCR \leq 2 mg/mg or urine protein \leq 2 g/24 h on 24-h urine collection.Dose reduce or interrupt cabozantinib treatment if UPCR $>$ 2 mg/mg on repeat UPCR testing or urine protein $>$ 2 g/24 h on 24-h urine collection. Continue cabozantinib on a reduced dose if UPCR decreases to $<$ 2 mg/mg. Consider interrupting cabozantinib treatment if UPCR remains $>$ 2 mg/mg despite a dose reduction until UPCR decreases to $<$ 2 mg/mg. Restart cabozantinib treatment at a reduced dose after a dose interruption.Repeat UPCR within 7 days and once per week. If UPCR $<$ 1 mg/mg on 2 consecutive readings, UPCR monitoring can revert to protocol-specific times. (Second reading is confirmatory and can be done within 1 week of first reading.) If UPCR remains $>$ 1 mg/mg and $<$ 2 mg/mg for 1 month or is determined to be stable ($<$ 20% change) for 1 month, check urine protein/creatinine per protocol or as clinically indicated.
\geq 3.5 mg/mg (\geq 395.9 mg/mmol)	
Interrupt cabozantinib treatment pending repeat UPCR within 7 days and/or 24-h urine protein.If \geq 3.5 mg/mg on repeat UPCR, continue to interrupt cabozantinib treatment and check UPCR every 7 days. If UPCR decreases to $<$ 2 mg/mg, restart cabozantinib treatment at a reduced dose and monitoring of urine protein/creatinine should continue weekly until the UPCR decreases to $<$ 1 mg/mg. If UPCR remains $>$ 1 mg/mg and $<$ 2 mg/mg for 1 month or is determined to be stable ($<$ 20% change) for 1 month, check urine protein/creatinine per protocol or as clinically indicated.

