8 STUDY CALENDAR

1 cycle = 3 weeks ± 3 days

Examination	Pre-screening ²³	Screening ¹	C1, 5, 9... Day 1 ²	C2, 6, 10... Day 1	C3, 7, 11... Day 1	C4, 8, 12... Day 1	End of Treatment ²⁰	Follow-up ²¹
Informed consent	X	X						
Medical history		X						
Eligibility criteria	X	X						
Vital signs, weight		X	X	X	X	X	X	
Height		X						
Physical examination ³	X	X	X	X	X	X	X	
ECOG performance status		X	X	X	X	X	X	
Viral Hepatitis Screening ⁴	X							
Smoking History		X						
Hematology ⁵	X	X	X	X	X	X	X	
Chemistry ⁶	X	X	X	X	X	X	X	
LDH, Lipase, Lipid Panel, GGT ⁷	X					X	X	
BNP ²²		X				X	X	
Urinalysis ⁸	X	X	X	X	X	X	X	
Coagulation ⁹	X					X	X	
Thyroid Function Test ¹⁰	X					X	X	
Pregnancy test ¹¹	X		X			X		
ECG ¹²		X				X		
Concomitant Medications					X			
Adverse Event Assessment					X			
CT Scans (c, a, p) ¹³	X					X ¹³	X	X ²¹
Bone Scans ¹⁴	X	X					X	X
Optional Tissue for Correlative Studies ¹⁵	X	(X) ¹⁵				X		
Optional Blood for Correlative Studies ¹⁶			X	X	X	X	X	
Optional Stool for Correlative Studies ¹⁷			X	X	X	X	X	
Optional Stool Questionnaire to accompany Optional Stool sample collection for Correlative Studies ¹⁷			X	X	X	X	X	
Cabozantinib ¹⁸			X	X	X	X		
Pembrolizumab ¹⁹			X	X	X	X		
Survival Follow Up								X ²¹

1. Screening procedures must be completed within 28 days prior to C1D1 ALL Pre-study/Screening procedures should be completed within 4 weeks of study enrollment - with the exception of laboratory tests which need to be completed within 14 days prior to study treatment.
2. Labs on C1D1 do not need to be repeated if conducted within 14 days of start of treatment
3. Physical Exam including oral examination
4. Hepatitis screening will be performed at screening if clinically indicated.
5. Hematology includes CBC with differential and platelets (must be completed within 2 weeks prior to study enrollment).
6. Chemistry includes Albumin, Alkaline Phosphatase, Aspartate Aminotransferase, Alanine Aminotransferase, Total Bilirubin, Calcium, Carbon Dioxide, Creatinine, Chloride, Glucose, Potassium, Protein, Sodium, Urea Nitrogen, phosphorus and magnesium (must be completed within 14 days prior to study enrollment at screening)
7. Additional Labs: Lactate Dehydrogenase, Lipase, Lipid Panel, Gamma Glutamyl Transferase, and should be collected at baseline and at every 4th cycle.
8. Urinalysis including urine protein/creatinine ratio on day 1 of each cycle. Both spot protein/creatinine and the 24 protein/creatinine evaluations are acceptable.

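### The UPCR entry limit in criterion 5.2.16 is printed as 2 mg/mg and as 113.2 mg/mmol, which differ two-fold by the protocol's own conversion in Table 7.7

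*Combined protocol and SAP*

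**What the plan says.** Section 5.2, item 5.2.16 (Renal), requires "Urine protein/creatinine ratio (UPCR) ≤ 2 mg/mg (≤ 113.2 mg/mmol", together with a condition on serum creatinine or calculated creatinine clearance. The item belongs to the Yes/No checklist in which a negative answer makes the patient ineligible, and the investigator signs to certify that all criteria are met.

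Table 7.7 in Section 7.1.1, on managing proteinuria during cabozantinib treatment, uses the same two units. Its first row is "≤ 1 mg/mg (≤ 113.1 mg/mmol" and its second is "> 1 and < 3.5 mg/mg (> 113.1 and < 395.9 mg/mmol". The table also uses 2 mg/mg as a threshold within the second row, but gives no mg/mmol figure for it.

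On measurement, note 8 to the Study Calendar (Section 8) asks for the ratio on day 1 of each cycle and adds: "Both spot protein/creatinine and the 24 protein/creatinine evaluations are acceptable". No reporting unit is prescribed. Section 4.3 names one institution and adds: "Up to two additional sites may be included".

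**The concern.** A limit printed in two units should give the same answer in both. Here the mg/mmol figure beside 2 mg/mg is almost exactly the figure that Table 7.7 prints beside 1 mg/mg, so one half of the criterion has to be wrong.

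This is an operative eligibility threshold, and the protocol itself treats proteinuria as a recognized risk of cabozantinib: Section 3.1.4 lists it among the medically important events and reports Grade 3 proteinuria in 3% of subjects in the earlier urothelial study. The trial also admits patients with creatinine clearance from 30 to below 60 ml/min. For a patient whose ratio lies between the two limits, the protocol does not settle whether enrollment is valid or is an exception to eligibility, which Section 15.9 requires to be reported promptly to the IRB. Sites working in different units could admit different patients.

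**Working it through.** The check is a linear unit conversion: UPCR in mg/mmol = k × UPCR in mg/mg.

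**Step 1. Take k from the protocol (Table 7.7).**
- Pair at 1 mg/mg: k = 113.1 / 1 = 113.10
- Pair at 3.5 mg/mg: k = 395.9 / 3.5 = 113.11

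The table agrees with itself: 3.5 × 113.1 = 395.85, printed as 395.9.

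**Step 2. Try to reproduce the figure in 5.2.16.**
- 2 × 113.10 = 226.2 mg/mmol; with the second factor, 2 × 113.114 = 226.2 mg/mmol
- The criterion prints 113.2 mg/mmol, so its figure is not reproduced.
- The factor implied by the criterion is 113.2 / 2 = 56.6, about half of Table 7.7's.

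**Step 3. Convert the printed mg/mmol figure back.**
- 113.2 / 113.1 = 1.001 mg/mg, against the 2 mg/mg printed.

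**Step 4. Size of the gap.**
- 226.2 / 113.2 = 1.998
- The two estimates of k differ by about 0.01% (113.114 / 113.10 = 1.0001), so rounding cannot produce a factor of two.

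**Step 5. Who is affected.**

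| Baseline UPCR | In mg/mmol (k = 113.1) | By the 2 mg/mg limit | By the 113.2 mg/mmol limit |
|---|---|---|---|
| up to about 1.0 mg/mg | up to 113.2 | pass | pass |
| 1.5 mg/mg (example) | 1.5 × 113.1 = 169.7 | pass | fail |
| 2.0 mg/mg | 226.2 | pass | fail |
| above 2.0 mg/mg | above 226.2 | fail | fail |

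The disagreement is confined to ratios above about 1.0 and up to 2.0 mg/mg.

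**The case against.** The conversion itself is not open to dispute; the case on the other side concerns how much it matters.

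- **Sites will probably work in mg/mg.** The named institution is in Utah. The same criterion gives the Cockcroft-Gault formula with creatinine in mg/dL, mg/mg is the leading figure with mg/mmol in parentheses, and the 2 mg/mg thresholds in Table 7.7 carry no mg/mmol equivalent. A site that reads only mg/mg would apply 2 without noticing a conflict. This makes divergence in practice less likely, and that stands. It does not show which limit was intended, because Table 7.7 also uses 1 mg/mg as a threshold, and the checklist prints both units without ranking them.
- **Table 7.7 does not strictly apply at baseline.** It covers proteinuria judged related to cabozantinib, which a pre-dose value cannot be. That stands, so the table serves here only as the source of the conversion. A baseline of 1 to 2 mg/mg would fall numerically in its second row, where no treatment change is required at or below 2 mg/mg.
- **UPCR may not decide eligibility.** The criterion joins UPCR, serum creatinine and creatinine clearance by an unbracketed and/or. On one reading, meeting the clearance limit would be enough regardless of UPCR. The more natural reading keeps UPCR mandatory with a choice between creatinine and clearance. The contradiction remains on either reading, but its effect on eligibility depends on the second.
- **The population is still largely defined.** Outside the 1 to 2 mg/mg band the two figures agree, the other organ-function criteria apply, and UPCR is repeated every cycle. That stands and limits the consequence to this band.

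**Conclusion.** The concern holds. By Table 7.7's conversion, the two halves of criterion 5.2.16 differ by a factor of 1.998: 226.2 against 113.2 mg/mmol, or 2 against 1.00 mg/mg. Patients above about 1.0 and up to 2.0 mg/mg are classified in opposite ways by the two figures, provided that UPCR is a mandatory part of the renal criterion. The finding of a contradiction rests only on figures in the protocol.

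The practical effect is narrow. The documents do not say how many patients fall in the band or whether any laboratory reports in mg/mmol, so the number affected could be zero. The ORR calculation and the sample size do not depend on it. It is nevertheless an error in a threshold that investigators must certify, and it should be corrected.

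**What to change.** Reconcile item 5.2.16 with Table 7.7 so that both units express one limit. There are two consistent forms:

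- keep 2 mg/mg and change the mg/mmol figure to 2 × 113.1 = 226.2; or
- keep the mg/mmol figure and change the mg/mg figure to 1, in which case 113.1 would match Table 7.7 exactly.

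The sponsor must decide which limit was intended; the documents do not settle it. In the same edit it would help to bracket the and/or in the renal criterion, so that it is clear whether UPCR is always required. If patients have already been enrolled, those with a baseline ratio above 1.0 and up to 2.0 mg/mg should be identified, so that their eligibility can be documented against the corrected limit.

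The cost is one number in the eligibility checklist, made in the next amendment. No analysis or sample-size text changes.

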Diagnosis and Main Eligibility Criteria	
Cisplatin-ineligible urothelial carcinoma
 
Key Inclusion Criteria:
 
• Histologically proven transitional cell or urothelial carcinoma (UC).• Metastatic (any N+ or M1) or locally advanced, unresectable (T4bN0) disease.• Measurable disease is required as determined by RECIST v1.1.• Cisplatin-ineligibility based on ≥ 1 of the following:
○ Estimated CrCl of between ≥ 40 and < 60 ml/min (CG formula)○ ECOG PS ≥ 2○ Hearing loss○ Baseline neuropathy○ Patient refusal 
Key Exclusion Criteria:
 
• Prior chemotherapy for metastatic/ advanced urothelial carcinoma.• Prior chemotherapy treatment for localized urothelial carcinoma that has been completed less than 6 months before registration.

	
• Small-cell or sarcomatoid component in histology.
Study Product, Dose, Route, Regimen	Pembrolizumab 200mg IV q 3 weeks with cabozantinib administered 40mg orally, with dose reductions to 20 mg daily. Subsequent dose reduction to 20 mg every other day to improve tolerability is allowed.
Duration of administration	Patients will receive therapy until treatment discontinuation criteria is met or until 12 months from start of therapy
Reference therapy	Study treatment will be compared to pembrolizumab as single agent.
Statistical Methodology	A 95% one-sided exact binomial confidence interval (Clopper-Pearson) will be calculated for ORR. With 35 evaluable subjects the lower bound of the 95% confidence interval will extend no more than 26% from the observed proportion. If there are 17 or more objective responses in 35 patients the confidence interval will exclude 32%. Secondary analyses will include an association of risk group (based on performance status and visceral metastasis) with PFS. Stratified Kaplan-Meier methodology will be used to associate risk group (based on performance status and visceral metastasis) with PFS.

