A population PK analysis was conducted in subjects with RCC who received repeated oral daily cabozantinib tablet dosing at 60 mg (with protocol-permitted dose reductions to 40 mg and 20 mg) combined with healthy subjects who received a single oral cabozantinib tablet dose of 20, 40, or 60 mg. This analysis indicated that for a white male subject, the predicted terminal plasma half-life of cabozantinib was approximately 99 h; the terminal phase volume of distribution (Vz) was approximately 319 L; and the CL/F at steady-state was estimated to be approximately 2.2 L/h. Female gender and Asian race were significant covariates on CL/F, and while the attributes were statistically significant, they were not deemed clinically meaningful given the magnitude of the effects.

Absorption and Distribution

Following oral administration of cabozantinib, median time to peak cabozantinib plasma concentrations (Tmax) ranged from 2 to 5 hours post-dose. Repeat daily dosing of cabozantinib at 140 mg for 19 days resulted in 4- to 5-fold mean cabozantinib accumulation (based on AUC) compared to a single dose administration; steady state was achieved by Day 15. Cabozantinib is highly protein bound in human plasma (99.7%). A high-fat meal increased Cmax and AUC values by 41% and 57%, respectively relative to fasted conditions in healthy subjects administered a single 140 mg oral cabozantinib dose.

Metabolism and Elimination

Cabozantinib is a substrate of CYP3A4 in vitro. Inhibition of CYP3A4 reduced the formation of the XL184 N-oxide metabolite by >80%. Inhibition of CYP2C9 had a minimal effect on cabozantinib metabolite formation (i.e., a <20% reduction). Inhibition of CYP1A2, CYP2A6, CYP2B6, CYP2C8, CYP2C19, CYP2D6 and CYP2E1 had no effect on cabozantinib metabolite formation. Within a 48-day collection period after a single dose of ¹⁴C- cabozantinib in healthy subjects, approximately 81% of the total administered radioactivity was recovered with 54% in feces and 27% in urine.

Specific Populations

Renal Impairment

Cabozantinib should be used with caution in subjects with mild or moderate renal impairment. No formal pharmacokinetic study of cabozantinib has been conducted in patients with renal impairment. The results of a population pharmacokinetic analysis suggested that mild to moderate renal impairment (creatinine clearance value <30 mL/min) does not have a clinically relevant effect on the clearance of cabozantinib.

Hepatic Impairment

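### Renal entry criterion (5.2.16): the creatinine alternative admits clearance below 30 mL/min under either grouping, and one literal grouping switches off the proteinuria limit

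*Combined protocol and SAP*

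**What the plan says.** The renal part of section 5.2.16 contains three conditions in one sentence: a UPCR limit of 2 mg/mg (also printed as 113.2 mg/mmol), serum creatinine of at most 2.0 × ULN, and a clearance limit. The first join is "mg/mmol) and serum creatinine"; the second is "ULN or calculated creatinine clearance ≥ 30 mL/min (≥ 0.5 mL/sec". There are no brackets, sub-bullets or commas to fix the grouping. Section 5.2.2, by contrast, sets its alternatives out as separate bullets with capitalised connectives.

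The figure of 30 mL/min appears once more in the eligibility list. Section 5.2.6 requires "Cisplatin-ineligibility based on ≥ 1 of the following", and the renal route is "Estimated creatinine clearance between ≥ 30 and < 60 ml/min (Cockcroft-Gault formula". The other four routes are performance status, hearing loss, neuropathy and refusal. For the same renal route the synopsis has "Estimated CrCl of between ≥ 40 and < 60 ml/min (CG formula".

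Table 7.7 governs proteinuria on treatment. It asks for no change in cabozantinib at UPCR up to 2 mg/mg, for reduction or interruption when a repeat value exceeds 2 mg/mg, and for interruption at 3.5 mg/mg or more. It equates 1 mg/mg with 113.1 mg/mmol.

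**The concern.** Section 5.2 is a signed yes/no checklist, and section 12 requires every criterion to be met before registration. A line that can be parsed in two ways does not tell a site, or a monitor checking for eligibility deviations under 15.9, what a yes means. Up to three centres may apply it.

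Two things are at stake. First, the plan does not say whether any lower clearance bound is meant for all patients, and as written none operates. Second, a literal reading lets in patients whose proteinuria already exceeds the level at which Table 7.7 acts on treatment. Toxicity is a secondary objective and at most 39 patients will be enrolled, so each patient is about 1/39 = 2.6% of the safety set. A handful of unintended entrants would visibly change the renal and proteinuria findings. The calculation of the primary endpoint is not affected.

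**Working it through.** **Logic.** Let U = UPCR within the limit, S = serum creatinine ≤ 2.0 × ULN, C = clearance ≥ 30 mL/min. The sentence can be read as

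- Grouping A: U and (S or C)
- Grouping B: (U and S) or C

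| U | S | C | A | B |
|---|---|---|---|---|
| yes | yes | yes | eligible | eligible |
| yes | yes | no | eligible | eligible |
| yes | no | yes | eligible | eligible |
| yes | no | no | not | not |
| no | yes | yes | not | eligible |
| no | yes | no | not | not |
| no | no | yes | not | eligible |
| no | no | no | not | not |

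Row 2 is the patient below 30 mL/min. That patient is eligible under both groupings, so brackets alone change nothing there. The groupings differ only in rows 5 and 7: UPCR over the limit with clearance of 30 or more. Under B, a patient with clearance 45 mL/min and UPCR 4 mg/mg is eligible, although Table 7.7 interrupts cabozantinib at 3.5 mg/mg.

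**Does section 5.2.6 block row 2?** No. Its bound of 30 applies only to the renal route. A patient below 30 can satisfy 5.2.6 through any of the other four.

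**Can row 2 occur?** The protocol's printed unit pair reproduces: 30 mL/min ÷ 60 = 0.5 mL/sec. Its Cockcroft-Gault formula is (140 − age) × weight / (creatinine × 72), times 0.85 for women. ULN is not given, so 1.0 to 1.3 mg/dL is assumed. Examples:

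- Man, 75 y, 70 kg, creatinine 2.4 mg/dL (2.0 × 1.2): 65 × 70 / (2.4 × 72) = 26.3 mL/min
- Woman, 75 y, 60 kg, creatinine 2.0 mg/dL (2.0 × 1.0): 65 × 60 / (2.0 × 72) × 0.85 = 23.0 mL/min
- Woman, 80 y, 60 kg: clearance is 30 at creatinine 60 × 60 × 0.85 / (72 × 30) = 1.42 mg/dL, so with ULN 1.0 the two limits disagree from just above 1.42 up to 2.0 mg/dL

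The grid is ages 65, 75 and 85, weights 60, 70 and 80 kg, and both sexes (18 profiles). Number with clearance below 30 mL/min:

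| Assumed ULN (mg/dL) | creatinine = 1.5 × ULN | creatinine = 2.0 × ULN |
|---|---|---|
| 1.0 | 1 of 18 | 9 of 18 |
| 1.1 | 4 of 18 | 14 of 18 |
| 1.2 | 8 of 18 | 15 of 18 |
| 1.3 | 9 of 18 | 17 of 18 |

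At 2.0 × ULN the clearances run from 15.0 to 41.7 mL/min across the four ULN values. At creatinine equal to ULN the effect all but disappears: the lowest value, at ULN 1.3, is 55 × 60 / (1.3 × 72) × 0.85 = 29.97.

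**Units of the UPCR limit.** With Table 7.7's factor, 3.5 × 113.1 = 395.85, which matches its printed 395.9. The same factor gives 2 × 113.1 = 226.2 mg/mmol, but 5.2.16 prints 113.2, and 113.2 / 113.1 = 1.0 mg/mg. A patient at 1.5 mg/mg (1.5 × 113.1 = 169.65 mg/mmol) passes in one unit and fails in the other.

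**The case against.** Four objections carry weight.

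*Grouping A is probably what was meant.* The hepatic bullet just above has the same shape: a bilirubin limit, *and* a transaminase limit, *or* a wider transaminase limit in metastatic disease. It makes sense only as bilirubin and (one or the other). Table 7.7's action above 2 mg/mg also fits an entry limit that always applies. This stands, so loss of the proteinuria limit is a drafting risk rather than the likely design.

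*A creatinine-or-clearance alternative is a legitimate choice.* This stands too. A reader might infer that 30 mL/min is a mandatory floor which the line breaches. The documents do not say so: 30 is one of two alternatives in 5.2.16 and part of one route of five in 5.2.6, and the synopsis has 40. What remains is that the three places do not show whether a general bound was intended.

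*The affected patient may be rare.* Because renal impairment is an entry route, a reader might take the patient below 30 as typical. That does not follow, since the renal route itself requires at least 30 and such a patient must enter by another one. The documents give no frequency for clearance below 30 or UPCR above 2.

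*There are safeguards.* Section 5.3.13 lets the investigator exclude patients for laboratory abnormalities that raise risk, and UPCR is measured on day 1 of each cycle. These soften the consequence but do not make the criterion readable.

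Section 3.1.2 settles nothing either way. Its sentence that "mild to moderate renal impairment (creatinine clearance value <30 mL/min) does not have a clinically relevant effect" pairs a label with a range that contradicts it, so it cannot be used to argue for or against enrolment below 30. Table 7.7 covers proteinuria only and should not be read as a set of clearance rules.

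**Conclusion.** The concern holds in this form. The renal line is ungrouped. Patients below 30 mL/min with creatinine within 2.0 × ULN and UPCR within the limit are admitted under both groupings, because of the *or* itself. A reader might blame the missing brackets for this, but they matter only for patients over the UPCR limit with clearance of 30 or more, and only there could two sites parsing the sentence differently reach different decisions.

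The gap between the creatinine and clearance limits is wide near the top of the creatinine range (9 to 17 of 18 profiles at 2.0 × ULN, 1 to 9 of 18 at 1.5 × ULN). These counts rest on the assumed ULN of 1.0 to 1.3 mg/dL and on illustrative ages and weights; they are not an estimate of how many enrolled patients would be affected. The twofold conflict between the units of the UPCR limit follows from the protocol's own figures and needs no outside assumption. No view is taken on which renal limit is clinically right.

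**What to change.** - Make UPCR a separately numbered checklist item, so that it applies to every patient.
- Write the creatinine/clearance alternative as its own item with explicit grouping.
- Have the sponsor reconcile 5.2.16, 5.2.6 and the synopsis, and state whether any lower clearance bound applies to all patients or only to the renal route to cisplatin-ineligibility. This review does not choose the bound.
- Reconcile the two units of the UPCR limit in 5.2.16 with the conversion in Table 7.7.

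The cost is a one-line amendment and a revised checklist. Sample size and analysis are untouched. Depending on what the sponsor decides, the eligibility of a few patients may change.
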